Appendix 5 Liver Safety: Suggested Actions and Follow-up Assessments

If a study participant is noted to have alanine aminotransferase or aspartate aminotransferase elevated 3 times or greater above upper limit of normal (ULN; new or worsening of preexisting), the abnormality should be recorded as an adverse event, regardless if clinical symptoms are present or not. If a study participant is noted to have alanine aminotransferase or aspartate aminotransferase 3 times or greater above ULN and total bilirubin > 2 ULN for which an alternative etiology has not been identified, the event should be reported as a serious adverse event. The Investigator must contact the Sponsor Medical Responsible for discussion (see Section 7.1 for details).

Appendix 6 Clinical Laboratory Tests**Table 20 Protocol-Required Clinical Laboratory Assessments**

Laboratory Assessments	Parameters						
Hematology	Platelet count		Mean corpuscular volume (MCV)	White Blood Cell Count with absolute and/or percentage (%): 
• Neutrophils• Lymphocytes• Monocytes• Eosinophils• Basophils			
	Reticulocytes						
	Hemoglobin		Mean corpuscular hemoglobin (MCH)				
	Hematocrit						
Coagulation	INR, prothrombin time, partial thromboplastin time (aPTT)						
Biochemistry	Blood Urea Nitrogen or Urea	Potassium	Aspartate aminotransferase	Bilirubin (total and direct)			
	Creatinine	Sodium	Alanine aminotransferase	Protein and albumin			
	Glucose	Calcium	Alkaline phosphatase				
	Gamma glutamyltransferase (gGT)	Lipase	Amylase				
Details of liver chemistry stopping criteria and required actions are given in Section 6.6.1 and Appendix 5 .							
Routine Urinalysis	
 • Specific gravity • pH, glucose, protein, blood, ketones by dipstick • Microscopic examination (if blood or protein is abnormal) 						
Other Screening Tests	
 • Serum and urine human chorionic gonadotropin pregnancy test (as needed for women of childbearing potential). 
Serology (with no preclinical signs of hepatotoxicity, hepatitis B surface antigen, hepatitis C virus antibody) to rule out active infection will be performed at the Investigator's discretion. HIV screening is optional at the Investigator's discretion unless required locally.
 
All study-required laboratory assessments will be performed by a central laboratory, except for safety laboratory assessments.
						

Appendix 7 Potential Variations in Study Intervention Schedules and Schedules of Activities

Additional schedules may also be evaluated at the discretion of the Sponsor and SMC.

Summary of alternate schedules of M4076 and changes to the Schedule of Activities in Part 1A (Table 21):

Table 21 Summary of Alternate Schedules of M4076

Part 1A	
Twice weekly	
Clinic visits	No change
M4076 administration	M4076 dosing is twice daily on Days 1 and 4 of each week (e.g., Mon, Thu).
PK sampling	No change
Three times weekly	
Clinic visits	No change
M4076 administration	M4076 dosing is on Days 1, 3 and 5 of every week (e.g., Mon, Wed, Fri).
PK sampling	-DLT Period Days 1 and 12: predose at 0 hours, postdose at 0.5, 1, 2, 3, 4, 6, 8 hours. -DLT Period Days 2 and 13: 24 hour (\pm 4 hour) postdose on D1 and D12 -3-week Periods Day 1 and subsequently every other 3-week Period: take two samples at start and end of visit, at least 1 hour apart.
4 days on/3 days off	
Clinic visits	No change
M4076 administration	M4076 dosing is on 4 consecutive days of a week (e.g., Mon, Tue, Wed, Thu)
PK sampling	-DLT Period Days 1 and 11: predose at 0 hours, postdose at 0.5, 1, 2, 3, 4, 6, 8 hours. -DLT Period Days 2 and 12: 24 hour (\pm 4 hour) post dose on D1 and D11 (to be taken prior to next dosing). -3-week Periods Day 1 and subsequently every other 3-week Period: take two samples at start and end of visit, at least 1 hour apart.
7 days on/7 days off	
Clinic visits	No change
M4076 administration	M4076 dosing on Days 1-7 followed by a 7-day drug holiday.
PK sampling	For DLT period starting with on weeks: -DLT Period Days 1 and 21: predose at 0 hours, postdose at 0.5, 1, 2, 3, 4, 6, 8 hours. -DLT Period Days 2 and 22: 24 hour (\pm 4 hour) post dose on D1 and D21 (to be taken prior next dosing). -3-week Periods Day 1 and subsequently every other 3-week Period: take two samples at start and end of visit, at least 1 hour apart. It is advisable to have all DLT periods for this scheme to start with 7 dosing days. However, for patients who start with 7 days off, the following sampling strategy applies:

	
-DLT Period Day 8, Day 15: predose at 0 hours, postdose at 0.5, 1, 2, 3, 4, 6, 8 hours. -DLT Period Day 9: 24 hour (\pm4 hour) post dose on D8 (to be taken prior to next dosing). -3-week Periods Day 8 and subsequently every other 3-week Period: take 2 samples at start and end of visit, at least 1 hour apart.

14 days on/14 days off	
Clinic visits	Days 1, 2, 14, and 15
M4076 administration	M4076 dosing on Days 1-14 followed by a 14-day drug holiday.
PK sampling	
-DLT Period Days 1 and 14: predose at 0 hours, postdose at 0.5, 1, 2, 3, 4, 6, 8 hours. -DLT Period Days 2 and 15: 24 hour (\pm4 hour) post dose on D1 and D14 (to be taken prior next dosing). -3-week Periods Day 1 and subsequently every other 3-week Period: take two samples at start and end of visit, at least 1 hour apart.
 
It is advisable to have all DLT periods for this scheme to start with 14 dosing days.
 
However, for patients who start with 14 days off, the following sampling strategy applies:
 
-DLT Period Days 15 and 21: predose at 0 hours, postdose at 0.5, 1, 2, 3, 4, 6, 8 hours. -DLT Period Day 16: 24 hour (\pm4 hour) post dose on D15 (to be taken prior next dosing). -3-week Periods Day 15 and subsequently every other 3-week Period: take two samples at start and end of visit, at least 1 hour apart.

D = Day; DLT = dose limiting toxicity; PK = pharmacokinetic.

Urine PK parameters will be assessed in Part 1B only

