4.1.1 Part 1A – M4076 Monotherapy Dose Escalation

Part 1A of the study will define the MTD and/or RDE of M4076 monotherapy in participants with advanced solid tumors for which no standard therapy is available.

The first dose escalation cohort of 3 participants will receive M4076 monotherapy at the starting dose of 100 mg administered orally once daily under fasting conditions (see Section 6.1 for fasting window information). For further dose escalation cohorts, an SMC will meet and review all available safety, PK and Pd data to provide recommendations on the DL for the next cohort. A Bayesian dose-toxicity model (Appendix 12) will assist the SMC in dose recommendations. For details of statistical considerations, see Section 9.

Potential DLs are: 100 mg (starting dose), 200 mg, 300 mg, 400 mg, 600 mg. A DL of 50 mg will be explored in case the starting dose of 100 mg is not tolerated. Depending on the observed toxicity profile and available PK and Pd, the SMC may decide on doses different to, or higher or lower from what is prespecified. The SMC may also recommend changing the dosing regimen to e.g. thrice weekly (daily dosing on Days 1, 3, and 5 of each week), twice weekly (daily dosing on Days 1 and 4 of each week), and/or schedules with holidays from study intervention (e.g., 3 days on/4 days off, 7 days on/14 days off, 14 days on/7 days off). More details on the SMC and dose escalation can be found in Section 6.6.1. The SMC operational details will be provided in an SMC Charter, which will be established prior to the start of recruitment. The details will include, but not limited to SMC membership, meeting frequencies, minimum requirements for data review, and responsibilities.

Dose escalation will proceed according to SMC recommendation until MTD and/or a safe RDE is determined and/or the SMC recommends ending dose escalation. The MTD and RDE are defined by the SMC. Target DLT probability for the MTD determination is 30%. In determining the RDE, the SMC will also consider PK, Pd and information on the safety and tolerability of the study intervention beyond the DLT period.

At least 6 participants are required to be treated at the MTD and/or RDE.

RDE cannot exceed MTD. If suggested RDE is below MTD, dose escalation will continue until MTD is reached (if applicable) or SMC decides ending dose escalation.

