6.1 Study Intervention Administration

Participants are planned to continue with study intervention (see [Table 8](#)) until documented disease progression, discontinuation due to adverse events, death or withdrawal from the study, whichever occurs earlier.

Fasting Window Definition

For Part 1A - The fasting window is defined as: 2 hours pre-dose to 1-hour post-dose in general, and 2 hours pre-dose to 4 hours post-dose on days where PK-time matched triplicate ECG will be collected. This fasting strategy facilitates more frequent daily dosing regimens and alleviates potential discomfort for advanced cancer patients during the dose escalation phase.

For Part 1B - The fasting window is defined as: 10 hours pre-dose to 4 hours post-dose.

Table 8 Study Intervention Details

Intervention Name	M4076
Type	Drug
Dose Formulation	Film-coated tablets
Unit Dose Strengths	50 mg
Dose Amount	M4076 will be administered orally, as planned, once daily per the dose escalation schema (Figure 2) and as determined by the SMC based on safety, tolerability, and preliminary PK and, if appropriate, Pd data. MTD/RDE to be determined. See Sections 4.1.1 and 6.6 for more information.

Frequency	Once daily; schedules may be adapted
Route of Administration	Oral
Use	Experimental
IMP/NIMP	IMP
Sourcing	Provided centrally by the Sponsor.
Packaging and Labeling	Study Intervention will be provided in participant kits containing M4076 tablets in blisters. Each kit will be labeled per country requirement.

IMP = investigational medicinal product; MTD = maximum tolerated dose; NIMP = non investigational medicinal product; Pd = pharmacodynamics; PK = pharmacokinetic; RDE = recommended dose for evaluation; SMC = safety monitoring committee.

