6.6.1 Safety Monitoring Committee

During the dose-escalation part (Part 1A) of the study, the SMC will evaluate the safety (including DLTs), tolerability, and available PK, to include at least predefined PK of the previous cohort, and available Pd data. The SMC will decide on dose escalation, de-escalation, additional enrolment on same DL, MTD, or suspension of enrolment. In cases where enrollment of the last participant in a dosing cohort is significantly delayed, the SMC may decide (based on available data) upon enrolment and dose for the next dosing cohort before all participants in a cohort have completed the DLT period. For this participant, the SMC will consider all available data and any subsequent emerging data at a subsequent meeting. An ad-hoc meeting will be convened if this participant experiences a DLT.

The SMC can recommend modifying the schedule of administration. SMC will review PK to determine if adjustment of schedule (to predefined alternative schedules as defined in [Appendix 7](#)) is appropriate during the dose escalation based on the collected data. The usual cohort size is 3 participants, but the SMC can decide to change the size of cohorts. Based on the observed toxicity profile and available PK and Pd, DL(s) that are different to, or higher or lower than the prespecified doses may be tested. The SMC may also recommend changing the dosing regimen.

During the Part 1B of the study, the SMC will monitor the safety and may recommend by consensus on continuation, expansion, and modifications of the study. The SMC may modify the frequency of meetings as deemed appropriate during the study.

The specific working procedures will be described in an SMC Charter, which will be established before first informed consent signed.

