9.4.2.1 Part 1A: Dose Escalation

Analyses to decide on dose escalation will be performed on the DLT set and will be based on available safety and preliminary PK data. To support the decision on dose escalation, the SMC will receive results of a Bayesian dose-toxicity model, including the recommendation of next DL. This Bayesian dose-toxicity model ([Neuenschwander 2008](#)) is further specified in [Appendix 12](#). For each SMC meeting, the model will be updated with the number of DLTs and evaluable participants per DL.

Potential DLs are: 100 mg (starting dose), 200 mg, 400 mg, 600 mg. However, the SMC may decide to have different, or additional DLs or skip DLs (total daily dose increases must not exceed 100% of the highest total daily DL currently considered safe). Based on the observed toxicity profile and available PK and Pd, DL(s) that are different to, or higher or lower than the prespecified DLs may be tested.

The dose suggested by the model for the next cohort will be based on [minimizing the Bayesian Risk](#).

The SMC may choose a different dose than suggested by the Bayesian escalation approach. Also, the SMC may decide to change the dosing regimen. In such a case the dose-toxicity model will be extended, or a separate model will be set up using the information from previous cohorts to define a new prior information for the new schedule.

The MTD will be defined by the SMC. The target DLT probability for the MTD is 30%.

Usually, decisions on dose escalation are taken once all participants of the most recent cohort have completed the DLT period or dropped out. In exceptional cases, however, the SMC may decide on the next cohort earlier, i.e., before the last participant of a cohort has finished the DLT

period (considering the model recommendation). Per definition of the DLT analysis set, participants who have not completed the DLT period are not included for update of the model, unless they experienced a DLT. However, data of such participants will be included at next SMC.

Details on analyses for SMC will be described in the SMC iAP.

[figure not shown]
Before first dosing, the assumed relationship between DL and toxicity is specified through the prior distribution. The prior distribution chosen for this study corresponds to the following (Table 18):

CCI

██████████	████	████	████	████	████
████	████	████	████	████	████
████	████	████	████	████	████

DLT = Dose limiting toxicity.

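### The optional twice-weekly schedule is once per dosing day in Protocol Section 4.1.1 but twice daily in Appendix 7 Table 21; the sponsor should confirm which is meant before it is used

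*Protocol*

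**What the plan says.** The base regimen in Table 8 (Protocol Section 6.1) is "Once daily; schedules may be adapted". Section 4.1.1 lets the SMC recommend another regimen and gives examples, including "twice weekly (daily dosing on Days 1 and 4 of each week") and "thrice weekly (daily dosing on Days 1, 3, and 5 of each week").

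Appendix 7 Table 21 summarises the alternate schedules. Its twice-weekly row reads "M4076 dosing is twice daily on Days 1 and 4 of each week". Its three-times-weekly row reads "M4076 dosing is on Days 1, 3 and 5 of every week", and its four-days-on row reads "M4076 dosing is on 4 consecutive days of a week". No row other than the twice-weekly one mentions two doses a day, and none gives a dose in mg.

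Section 6.6.1 gives the appendix standing: "SMC will review PK to determine if adjustment of schedule (to predefined alternative schedules as defined in" Appendix 7) is appropriate. Appendix 7 also allows schedules beyond those it lists. On a change of regimen, Section 9.4.2.1 says: "In such a case the dose-toxicity model will be extended, or a separate model will be set up". Appendix 12 has changes needed for a new regimen recorded in the SMC charter.

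**The concern.** One named schedule has two definitions that differ by a factor of two in the number of doses. Neither place says whether a twice-daily dose would be a full dose given twice or a daily dose divided in two.

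This is a dosing rule in a first-in-human trial, held in the appendix to which the SMC is directed. If a site followed Table 21 while the SMC had Section 4.1.1 in mind, participants could receive double the intended amount on each dosing day. The ambiguity also reaches the planned cumulative dose. That figure is the denominator for the 80% evaluability rule of the DLT analysis set (Protocol Section 9.3, SAP Section 8.1) and for compliance in SAP Section 9.

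**Working it through.** The documents state no administration count, so there is no figure of theirs to reproduce. The check is a direct count.

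**Inputs**
- DLT period: 21 days (Protocol Section 6.6.2).
- Dosing days: Days 1 and 4 of each week (Section 4.1.1 and Table 21 agree on this).
- Doses per dosing day: one under Section 4.1.1, reading its daily dosing as one administration; two under Table 21.
- D: mg per administration. No document sets it for any alternate schedule.

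**Count.** Days 1 and 4 of each week over 21 days are study days 1, 4, 8, 11, 15 and 18, which is 6 dosing days.
- Section 4.1.1: 6 × 1 = 6 administrations.
- Table 21: 6 × 2 = 12 administrations.

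**Drug given in 21 days**

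| Reading | Per dosing day | 21-day total | Share of once-daily dosing (21D) |
|---|---|---|---|
| Section 4.1.1 | D | 6D | 6/21 = 29% |
| Table 21, dose not split | 2D | 12D | 12/21 = 57% |
| Table 21, daily dose split | 2 × D/2 = D | 12 × D/2 = 6D | 29% |

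**Against the neighbouring schedules, assuming the same D.** Three times weekly falls on days 1, 3, 5, 8, 10, 12, 15, 17 and 19: 9 administrations (9/21 = 43%). Four days on, three off gives 4 × 3 = 12 (57%). Twice weekly is then 6/9 = 0.67 times the three-times-weekly total under Section 4.1.1, and 12/9 = 1.33 times under Table 21 unsplit.

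**Effect on the 80% rule, only if a cohort is planned on one reading and dosed on the other.** Take 300 mg per administration as an illustration.
- Planned dose: 6 × 300 = 1,800 mg or 12 × 300 = 3,600 mg.
- 80% thresholds: 1,440 mg or 2,880 mg.
- Dosed fully per Section 4.1.1 against a Table 21 plan: 1,800/3,600 = 50%, below the threshold.
- Dosed per Table 21 against a Section 4.1.1 plan: 3,600/1,800 = 200%, above the 120% limit at which SAP Section 14 removes a participant from efficacy summaries.

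**Which reading the rest of the text supports**
- For once daily: the row is headed as twice weekly; the base frequency is once daily; and Section 4.1.1 uses the same construction for three times weekly, where Table 21 has no twice-daily wording.
- For more than one dose a day: Section 6.1 justifies the short Part 1A fasting window partly as making it easier to dose more often, and the escalation cap in Section 9.4.2.1 and Appendix 12 is set on total daily dose.
- Not decisive: the row leaves PK sampling unchanged. Table 3 has no sample around a second daily dose, which might suggest once daily. But Table 3 also treats Days 2 and 9 as dosing days, and they are not dosing days on either reading.

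**The case against.** The strongest case on the other side is that little follows from the conflict. Appendix 7 is headed as potential variations, its table is a summary without mg levels, and other schedules are allowed. The SMC would have to choose the schedule and set the dose, the model would be extended or rebuilt, and needed changes would go into the charter. An SMC doing this would very likely notice the discrepancy. All of that stands, and it is why the point is minor. It does not remove the conflict: those steps govern the dose and the model, and none says which definition of the schedule applies.

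A reader might infer more than the documents support, in four ways.

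- *That twice daily is simply a slip.* The balance of wording leans that way, but Section 6.1 and the total-daily-dose cap point the other way, so the intent is for the sponsor to confirm.
- *That Table 21 doubles exposure.* It does so only if the dose per administration is unchanged, which no passage says. Nor does the literal row by itself breach the cap. If D is the highest daily dose considered safe, going to 2D is a (2D − D)/D = 100% increase, the largest step allowed.
- *That Section 4.1.1 and Table 21 otherwise match.* They agree on three times weekly, but their on/off examples differ (3/4, 7/14 and 14/7 days against 4/3, 7/7 and 14/14). Section 4.1.1 offers its list as examples, so those differences are not contradictions.
- *That DLT evaluability or efficacy results are at risk now.* This needs a cohort planned on one reading and dosed on the other. SAP Section 9 also bars moving a participant to a level with a different dosing scheme, and no twice-weekly levels are given.

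**Conclusion.** The two definitions conflict as written: 6 against 12 administrations in the 21-day DLT period. The difference in drug is twofold if the dose per administration is unchanged and nil in total if the daily dose is split. The comparison with three times weekly rests on the further assumption of equal D across schedules.

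Confidence is high that the conflict exists; the documents do not settle which side should change. The severity is minor. The once-daily escalation, the current Bayesian model and Part 1B are unaffected. No passage shows that a twice-weekly cohort was opened, and the added 300 mg level is described in Section 1.2 as once daily.

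**What to change.** Before any twice-weekly cohort opens, the sponsor should confirm the intended schedule and make one of two edits:

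1. If once daily is meant, change the Table 21 row to once daily on Days 1 and 4 of each week.
2. If twice daily is meant, change Section 4.1.1 to say so, and state the mg per administration and whether the daily dose is split. The unchanged PK sampling in that row should then be checked as well, because Table 3 has no samples around a second dose.

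The choice is clinical and belongs to the sponsor and the SMC. The first edit costs one line of wording and the second a few, with no new visits, data or participants. If a twice-weekly cohort has already been treated, the sponsor should also record which reading was used.

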1.3.1 Part 1A – M4076 Monotherapy Dose Escalation (Daily Dosing)

The schedule of events for Part 1A are provided in [Table 1](#).

The Part 1A fasting window is defined as: 2 hours predose to 1-hour postdose in general, and ~~C~~ hours predose to 4 hours postdose on days where PK-time matched triplicate ECGs are collected.

~~C~~
I

Table 1 Schedule of Activities: M4076 Monotherapy Dose Escalation (Daily Dosing), Part 1A

Assessments and Procedures	Screen (D -28 to -1)	DLT Period (21 days)					Subsequent 3-week Periods (21 days)			End of Study Intervention Visit	Safety Follow up/ Discontinuation Visit	Notes
Day		1	2	8	9	15	1	8	15	Within 7 days after last dose	30 days after last dose	
Visit Window (days)		-1								+7	+/- 7	Day 1 assessments that could be completed on Day -1 are limited to physical examination, height/weight, and ECOG performance status.
Study Site Visits	X	X	X	X	X	X	X	X	X	X	X	Starting Cycle 4, visits at Day 8 and Day 15 are optional
Written informed consent	X											
Inclusion / Exclusion Criteria	X											
Medical History (includes substance usage); Demography	X											Substances: tobacco use only.
Hepatitis B and C tests	X											To rule out active infection, performed at the Investigator's discretion. See Appendix 6 for details.
Optional HIV Screening	X											HIV testing is optional at the Investigator's discretion unless required locally.

Assessments and Procedures	Screen (D -28 to -1)	DLT Period (21 days)					Subsequent 3-week Periods (21 days)			End of Study Intervention Visit	Safety Follow up/ Discontinuation Visit	Notes
Day		1	2	8	9	15	1	8	15	Within 7 days after last dose	30 days after last dose	
Visit Window (days)		-1								+7	+/- 7	Day 1 assessments that could be completed on Day -1 are limited to physical examination, height/weight, and ECOG performance status.
Serum Pregnancy Test (WOCBP only)	X									X		See Section 8.3.5.
Urine Pregnancy Test (WOCBP only)		X				X						Urine β -hCG results must be available prior to M4076 dosing.
Physical Examination	X	X		X	X	X				X	X	See Section 8.2.1.
Height and Weight	X	X				X				X	X	Collect height at Screening only.
Imaging Disease Assessment (CT/MRI)	X	X (at the end of every 6 weeks for the first 24 weeks, then every 12 weeks)								X		Tumor assessment according to RECIST 1.1 until disease progression, end of study, or death, whichever is earlier. See Section 8.1 for details of imaging.

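### Table 21 sets the second PK profile of 7 on/7 off participants who start off drug on Day 15, a day on which they receive no dose

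*Protocol*

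**What the plan says.** Appendix 7, Table 21 defines the 7 on/7 off schedule as "M4076 dosing on Days 1-7 followed by a 7-day drug holiday". It has two sampling rules, depending on which week comes first.

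- **On-first:** "DLT Period Days 1 and 21: predose at 0 hours, postdose at 0.5, 1, 2, 3, 4, 6, 8 hours", with 24-h samples on Days 2 and 22.
- **Off-first:** "DLT Period Day 8, Day 15: predose at 0 hours, postdose at 0.5, 1, 2, 3, 4, 6, 8 hours", with one 24-h sample on Day 9. That sample is tied to the Day 8 dose and is to be drawn before the next dose.

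Table 21 adds that DLT periods on this schedule should preferably start with the dosing week. Clinic visits for 7 on/7 off are left as in Table 1, where the DLT-period visit days are 1, 2, 8, 9 and 15. Section 6.6.1 refers to the Appendix 7 schedules as the predefined alternatives that the SMC may adopt after reviewing PK.

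**The concern.** The second full profile in each schedule is there to describe exposure after repeated dosing. It needs a predose sample and then samples timed from a dose. In the off-first variant the second profile is placed one day after the dosing block ends. A site following the rule would collect a predose sample with no dose to follow, and seven postdose samples with no dose to time them from.

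At stake is the multiple-dose part of the secondary objective on single- and multiple-dose PK, for these participants only. It is also information that the SMC would want when judging a regimen it had just switched to, since Section 6.6.1 has it review PK from the previous cohort.

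**Working it through.** No power or sample-size figure is involved. The check is a day count. The plan's stated item is Day 15 as the second profile day.

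**Inputs**

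- Dosing cycle of 7 days on and 7 days off, 14 days in all (Table 21).
- DLT period of 21 days (protocol Section 6.6.2).
- Full profile = 1 predose + 7 postdose samples (0.5, 1, 2, 3, 4, 6, 8 h) = 8 samples (Table 21).
- Off-first: profiles on Days 8 and 15, one 24-h sample on Day 9 (Table 21).

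**Step 1: dosing calendar.** Off-first means off on Days 1–7, on on Days 8–14, off on Days 15–21, and on again from Day 22. The Day 9 line confirms this, because it treats Day 8 as a dose day with a further dose to follow. Day 15 is therefore off drug.

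**Step 2: can any alignment rescue Day 15?** Days 8 and 15 are 7 days apart, exactly half of a 14-day cycle, so one is always on and the other off. This was checked for all 14 possible starting points of the cycle and held in each. Since Day 8 is a dose day, Day 15 is not.

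**Step 3: compare with the other cyclic variants in Table 21.**

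| Variant | Dosing days up to Day 22 | Profile days | Profile days without a dose |
|---|---|---|---|
| 7/7 on-first | 1–7, 15–21 | 1, 21 | none |
| 7/7 off-first | 8–14, 22 | 8, 15 | 15 |
| 14/14 on-first | 1–14 | 1, 14 | none |
| 14/14 off-first | 15–22 | 15, 21 | none |

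The weekly schedules (twice weekly, three times weekly, 4 on/3 off) also have no profile on a day without a dose. The off-first 7/7 rule is the only one that fails. On-first 7/7 profiles Day 21, the 7th dose of the block on Days 15–21. The matching day off-first is Day 14, the 7th dose of the block on Days 8–14.

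**Step 4: size.**

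- DLT-period samples off-first: 8 (Day 8) + 1 (Day 9) + 8 (Day 15) = 17.
- Samples timed to a dose that is not given: 8 of 17 = 47%.
- Last dose is on Day 14. With the same dosing time each day, the Day 15 predose sample is at about 24 h and the 8-h sample at about 24 + 8 = 32 h after it.
- Multiple-dose profiles obtained in the DLT period: 0 instead of 1.

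**Step 5: draw count with the profile moved to Day 14.** 8 (Day 8) + 1 (Day 9) + 7 (Day 14 without 0.5 h) + 1 (24-h sample on Day 15) = 17, the same as now.

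**The case against.** **The group may not exist.** Protocol Section 6.6.2 counts the DLT period from the first dose, and SAP Sections 9 and 9.3 do the same. On that definition Day 1 is a dose day and nobody begins a DLT period with a week off. The off-first text could instead have been meant for a later period: on-first participants are off drug on Days 22–28, so their second 3-week period does open with 7 days off. They would already have profiles on Days 1 and 21, and no multiple-dose profile would be missing.

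This objection limits the harm, and the case may never arise. It does not make the rule right. Table 21 labels the rule as applying to the DLT period. On the later-period reading the profile days become study Days 21 + 8 = 29 (on drug) and 21 + 15 = 36 (off drug), so the second profile still has no dose.

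**The protocol can absorb it.** Section 4.1.1 lets the Schedule of Activities be adjusted to get PK timing right, and Section 8.5 allows sampling times to move if draws are not added. These clauses permit a correction but do not make one. The fallback in the note to Table 3 does not help: it offers Days 15 and 16, both off drug here, or Days 1 and 2 of the second period, which are the first two doses after a week off. Later periods call for only two samples per visit.

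**The Day 15 samples have some value.** They give a 24-h concentration after the seventh dose and early elimination data. That stands. What is missing is the peak and the 0 to 8 h curve.

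**Conclusion.** The Day 15 entry is wrong as written, and the consequence is minor. For off-first 7/7 participants, 8 of 17 DLT-period samples are timed to a dose that is not given, so no multiple-dose Cmax or 0 to 8 h curve is obtained. This rests on the literal 7/7 calendar; the 24 to 32 h figure also assumes a constant dosing time. The impact is small because the schedule is used only on an SMC decision and off-first starts are discouraged.

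Two stronger inferences are not supported.

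- A reader might infer that the Day 15 entry alone is what prevents the linearity index and both accumulation ratios from being calculated. SAP Section 16.1.5.1 limits all three to Day 8 of Part 1A. In this variant Day 8 is the first dose, so the SAP as it stands plans none of them here, wherever the second profile is placed.
- A reader might infer that samples will be lost in other schedules because their PK days are not in the visit row. For example, three times weekly asks for "DLT Period Days 1 and 12: predose at 0 hours, postdose at 0.5, 1, 2, 3, 4, 6, 8 hours" while its visits stay as in Table 1. The PK rows name every sampling day, and the note to Table 3 already allows PK on Day 16, outside the visit grid. No loss follows; that is a matter of table layout and not part of this point.

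**What to change.** 1. In Table 21, 7 on/7 off, off-first rule: replace Day 15 with Day 14 as the second profile day, and add a Day 14 visit for this variant.
2. Take a 24-h sample at the existing Day 15 visit and drop the 0.5-h point on Day 14. The base Day 8 profile in Table 3 has no 0.5-h point either. Draws stay at 17, as Section 8.5 requires.
3. Do not plan on reusing the predose value as the 24-h value. SAP Section 16.1.5.1 allows this only at steady state, for a missing sample, and after agreement with the sponsor. It is a fallback and no reason to leave the sample out of the plan.
4. If the linearity index and accumulation ratios are wanted in this variant, change the SAP restriction from Day 8 to the second-profile day of the schedule in use.
5. If the sponsor confirms that an off-first start cannot occur, because the DLT period begins with the first dose, delete the off-first rule. Steps 1 to 4 are then unnecessary for this variant.

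The cost is a wording change in one table, one extra visit per affected participant, no extra blood draws and, if step 4 is taken, a one-line SAP edit.
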